Within our Division, the surgical procedure of choice to treat pelvic organ prolapse is a total vaginal hysterectomy with concurrent vaginal native tissue prolapse repairs. As standard practice, patients are kept overnight in the hospital for observation and a CBC is collected the morning on POD1. Studies in the gynecology literature have looked at the utility of routine CBC on patients after elective gynecologic surgery in general, total laparoscopic hysterectomy, minimally invasive sacrocolpopexy with or without concurrent hysterectomy, but none have looked specifically at our patient population having a vaginal hysterectomy with vaginal prolapse repairs.^{2,6,7,10}

Our goal is to show that routine collection of a CBC on POD1 in asymptomatic patients after vaginal hysterectomy with prolapse repair is unnecessary. If this is found, we could stop routine CBC collection which is a bothersome procedure for many patients and an added expense contributing to high health care costs.

Research Plan:

Study Design: Retrospective chart review

Setting of Study: TriHealth Epic platform at one of the various clinical locations.

Participants: All patients who underwent a total vaginal hysterectomy with concurrent vaginal native tissue prolapse repairs performed by one of four fellowship trained urogynecologists at TriHealth between 10/1/2014 and 10/1/2019. The patients will be identified by CPT codes in the EPIC electronic medical record.

Inclusion Criteria:

Total vaginal hysterectomy with or without bilateral salpingectomy/oophorectomy (CPT 58260, 58262, 58263, 58270, 58290, 58291, 58292, 58294)

At least one of the following vaginal native tissue prolapse repairs

Apical repair with uterosacral ligament suspension (CPT 57283)

Apical repair with sacrospinous ligament fixation (CPT 57282)

Anterior repair (CPT 57240, 57260, 57284, 57285, 57250)

Posterior repair (CPT 45560, 56800, 56810, 57200, 57210, 57250)

Age >18

Surgery by one of four fellowship trained urogynecologists at TriHealth

Exclusion Criteria:

Concomitant surgical procedure by a second surgeon

Malignancy identified at the time of surgery or active malignancy

Cases converted to open hysterectomy or prolapse repairs

Prolapse repair completed robotically

Prolapse repair completed with mesh

Known coagulopathy

Patient on long term preoperative anticoagulant medication (Arixtra, Coumadin, Eliquis, Heparin, Lovenox, Pradaxa, Savaysa, Xarelto)

Sample Size:

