Similar retrospective studies included between 629-1105 patients in their chart review.^{2, 6, 7, 11} Based on the number of vaginal hysterectomies performed by our department annually, we anticipate five years of data collection will provide a comparable study size for this review. Our anticipated sample size will be approximately 800 patients.

Data Collection: Please see attached data collection sheet

- Charts of all patients having a total vaginal hysterectomy by one of our four fellowship trained urogynecologists during the study time frame will be identified and analyzed for inclusion and exclusion criteria.
- All charts meeting inclusion criteria will be included in the analysis.
- Each chart will be reviewed and the following variables collected for analysis:
 - Type(s) of prolapse repair(s)
 - Additional procedure for urinary incontinence at the same time as hysterectomy and prolapse repair – yes/no
 - Preoperative CBC collected within 30 days of surgery – yes/no
 - Preoperative hemoglobin
 - CBC collected the morning of POD1 – yes/no
 - POD1 hemoglobin
 - Change in hemoglobin from preoperative to postoperative collection
 - Change in hemoglobin level ≥ 2 – yes/no
 - Postoperative hemoglobin ≤ 10 – yes/no
 - More than one postoperative hemoglobin obtained – yes/no
 - Patient with objective signs of anemia (*persistent hemodynamic changes: pulse >100 beats per minute, blood pressure <90/60*) – yes/no
 - Patient with subjective signs of anemia (*dizziness, lightheadedness, weakness, pale, cool, diaphoretic*) – yes/no
 - Blood transfusion – yes/no
 - Estimated blood loss
 - IVF volume received intraoperatively
 - Length of surgery (in minutes)
 - Prophylactic heparin given preoperatively – yes/no
 - General demographic data including: name, DOB, age, race, BMI, medical comorbidities, parity, smoking history, menopausal status
 - Preoperative aspirin use – yes/no
 - Preoperative antiplatelet medication use (i.e.: Brilinta, Effient, Plavix) – yes/no
 - Stage of pelvic organ prolapse at preoperative appointment
 - Prior abdominal or pelvic surgery – yes/no
 - Patient readmitted within 30 days of surgery – yes/no

- Patient seen in emergency department within 30 days of surgery – yes/no
- Length of hospital stay (in days)
- Delay in discharge due to CBC results – yes/no

Intervention or experimental aspect of the study:

- No intervention will occur as part of this study.

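### Signs of anemia and POD1 hemoglobin are abstracted in the same chart review with no masking or staging described, so the symptomatic/asymptomatic split is not protected from result-aware coding

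*Combined protocol and SAP*

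**What the plan says.** The Research Plan gives "Study Design: Retrospective chart review". Data Collection describes one review per chart: "Each chart will be reviewed and the following variables collected for analysis". A single list follows. It includes the preoperative and POD1 values, "Change in hemoglobin from preoperative to postoperative collection", two threshold flags, and two yes/no sign items.

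- Objective signs are defined as "persistent hemodynamic changes: pulse >100 beats per minute, blood pressure <90/60". The limits are numeric, but what counts as persistent is not stated.
- "Patient with subjective signs of anemia" is followed by six descriptive terms. No rule says what wording in a note, or how many mentions, makes a yes.

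No section says who abstracts the charts, in what order, whether the abstractor is masked to the laboratory result, or whether a second reader checks the signs. The form itself is deferred: "Data Collection: Please see attached data collection sheet". That sheet is not in the text available for review.

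Statistical Analysis uses the sign label twice. It is the grouping variable in a Student's t-test on hemoglobin change, and the outcome of a multiple logistic regression. That section does not say whether symptomatic means objective signs, subjective signs or either. Background gives the purpose the label serves: "Our goal is to show that routine collection of a CBC on POD1 in asymptomatic patients" is unnecessary.

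**The concern.** The grouping variable rests partly on judgment, and the quantity compared between the groups comes from the same review. A reviewer who knows that a hemoglobin is low may search the notes harder for weakness or pallor, and accept a marginal entry more readily, than for a woman whose value is unremarkable. This moves women with larger drops into the symptomatic group and enlarges the difference that the t-test examines. The team has stated the conclusion it hopes to reach, and the error would run toward it.

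This is separate from when the sign occurred. A sign charted before the CBC result can still be coded selectively by someone who reads the chart afterwards with the result known. Once the label has been coded that way, no later analysis can recover the label that masked coding would have given.

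**Working it through.** **The plan's own figure.** There is no power calculation to reproduce. Sample Size gives about 800 patients, from five years of cases (800/5 = 160 per year) and from similar studies of 629 to 1105. No alpha, power, effect size or SD is given. The 800 is not disputed and is used below only for scale.

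**Inputs.** From the documents: n = 800, and the cut-off of 10 g/dL in Statistical Analysis. Assumed, because the documents give none of these: preoperative hemoglobin N(13, 1); drop N(2, 1), independent of it; true signs in 10%, unrelated to hemoglobin; and a fraction r of sign-free women with POD1 hemoglobin below 10 coded as symptomatic because the result is known, with r = 5%, 10% or 20%.

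**Step 1: women below 10.** POD1 is N(11, √2), so p = Φ(−1/√2) = 0.240. Their mean excess drop over 2 g/dL is k = (1/√2) × φ(1/√2)/p = 0.7071 × 0.3107/0.2398 = 0.916.

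**Step 2: share of all charts recoded.** a = 0.9 × p × r.

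**Step 3: spurious difference in mean drop.** D = a·k/(0.1 + a) + a·k/(0.9 − a). The first term is the rise in the symptomatic mean, the second the fall in the asymptomatic mean. With the drop SD of 1, the standard error is about √(1/n₁ + 1/n₂), where n₁ = 800(0.1 + a) and n₂ = 800 − n₁.

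**Step 4: share of the asymptomatic group below 10.** (0.9p − a)/(0.9 − a). Without recoding it is 24.0%.

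| r | Charts recoded (800a) | Symptomatic mean shift | Asymptomatic mean shift | D (g/dL) | SE | Asymptomatic below 10 |
|---|---|---|---|---|---|---|
| 5% | 8.6 | +0.089 | −0.011 | 0.100 | 0.113 | 23.1% |
| 10% | 17.3 | +0.163 | −0.023 | 0.185 | 0.108 | 22.1% |
| 20% | 34.5 | +0.276 | −0.046 | 0.322 | 0.101 | 20.1% |

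In 4,000 simulated studies per setting, a two-sided 0.05 t-test rejected a true null in about 5% with no recoding, and in 15%, 40% and 89% at the three values of r.

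**Sensitivity to the assumptions.** A second simulation used a drop of mean 1.8 and SD 1.0, with recoding triggered by a drop of 2 or more. The three columns on the right are for true sign shares of 5%, 10% and 20%.

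| Recoding of sign-free women with drop ≥ 2 | Charts of 800 | Rejection, signs 5% | Signs 10% | Signs 20% |
|---|---|---|---|---|
| 1% | about 3 | 0.07 | 0.07 | 0.06 |
| 2% | about 5 to 6 | 0.15 | 0.10 | 0.07 |
| 5% | about 13 to 16 | 0.53 | 0.33 | 0.18 |

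At 5% recoding the spurious differences were 0.28, 0.17 and 0.09 g/dL. The effect is negligible at about three charts. At about fifteen it ranges from modest to serious.

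**The case against.** The strongest reply is that the documents do not show that anyone codes signs with the hemoglobin in view. The data sheet is missing from the text, and no abstractor or order is named. This stands. A reader might infer that the split is not independent of the result; the text supports only that its independence is not protected.

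Four further inferences are tempting and do not hold.

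- **List order.** The laboratory items precede the sign items, which might suggest that they are coded first. But demographics, preoperative aspirin and prolapse stage come near the end, so the list is an inventory. Transfusion is listed after both sign items.
- **Discharge delay.** "Delay in discharge due to CBC results – yes/no" needs judgment, but it is not part of the split, and it cannot be coded without knowing the CBC. Its lack of attribution criteria is a different matter.
- **Transfusion and low hemoglobin.** Statistical Analysis names no test of either against signs. The logistic regression does not name hemoglobin as a factor, so an odds ratio between the two would belong to no stated analysis.
- **Asymptomatic women made to look much safer.** The working shows otherwise. Their mean drop shifts by at most 0.05 g/dL and their share below 10 by at most 4 percentage points. The contrast moves mainly through the small symptomatic group.

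It is also fair that numeric limits leave little discretion in the objective signs, that every recoding rate is assumed, and that at 5% recoding the spurious difference is smaller than its standard error. These points limit the size of the concern. They do not supply the missing safeguard.

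**Conclusion.** The concern holds as a lack of protection, not as a demonstrated bias. One chart review collects both the judgment-based signs and the hemoglobin, no masking or staging is described, and the split so formed is tested against hemoglobin change. The exposure lies in the subjective signs and in the word 'persistent'. The likely direction is an inflated difference, in favour of the stated goal.

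The size cannot be known from the documents. Under the assumptions above, recoding roughly 1% to 4% of charts (8.6/800 to 34.5/800) yields 0.10 to 0.32 g/dL where the true difference is zero, with little change within the asymptomatic group. The point therefore bears on the t-test. The logistic regression shares the same label, but its bias was not sized here. A cheap change made before abstraction is worthwhile; nothing here invalidates the design.

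**What to change.** Before abstraction starts:

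1. State whether symptomatic means objective signs, subjective signs or either, and write a coding rule for 'persistent' and for each subjective term.
2. Have the same reviewer code objective signs from the vital-sign flowsheet and subjective signs from the notes before opening laboratory or transfusion data, and lock those columns.
3. Then enter the hemoglobin values, or merge a laboratory export by the Subject ID that Privacy Information already provides for.
4. Flag charts whose notes reveal the hemoglobin and report their number.
5. As the sensitivity analysis, repeat the t-test with groups defined by objective signs only. Do not rely on dropping flagged charts: if low values are quoted more often, that exclusion selects on the hemoglobin itself.

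If staging proves unworkable, report unmasked abstraction as a limitation and keep step 5.

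**Cost.** A reordered data sheet and one laboratory export, with no additional reader. Abstraction takes somewhat longer. The timetable allows four weeks, about 40 charts a day for 800 if that means 20 working days, so the extra time should be checked. Masking will be imperfect where notes quote the value, and it gives no protection against symptoms that clinicians charted after seeing the CBC.

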Date	11/13/2019
Title	Clinical Utility of Postoperative Hemoglobin Testing Following Vaginal Hysterectomy and Reconstruction for Symptomatic Pelvic Organ Prolapse
Principle Investigator	[name]
Sub-Investigators	[name]
Research Specialist	[name], MS
Department	Urogynecology
Hatton #	19-111

Introduction:

- Obtaining a complete blood count (CBC) on post-operative day (POD) 1 to assess postoperative hemoglobin levels is routine practice at our institution after pelvic reconstructive surgery.
- There is minimal data supporting this practice. Multiple studies throughout the gynecology literature suggest that this is not a necessary or cost effective strategy to assess for postoperative anemia. ^{2,6,9,11}
- Most patients who require blood transfusion or reoperation for bleeding will show clinical signs of anemia. ^{2, 6, 7, 11} It is necessary to consider the entire clinical picture before initiating blood transfusion for postoperative anemia. ¹
- Although the individual cost of each lab test is low, the cumulative cost of these tests is substantial. ^{2,9}
- The procedure of choice for prolapse repair by Cincinnati Urogynecology Associates, TriHealth Inc. is a vaginal hysterectomy (TVH) with concurrent apical, anterior, and posterior compartment native tissue repairs as indicated. A review of the literature failed to identify any studies that have looked specifically at the utility of postoperative CBC after vaginal hysterectomy with prolapse repairs.

Purpose of Study

- To determine if checking a routine CBC results in clinically relevant changes to patient care in women undergoing pelvic reconstructive surgery with vaginal hysterectomy for treatment of pelvic organ prolapse.

Hypothesis or Research Question:

- We hypothesize that there is minimal utility in the routine collection of POD1 CBC in patients undergoing TVH during vaginal prolapse repairs.
- We also hypothesize that the overall blood transfusion rate of our pelvic reconstructive patients is low, and that a more selective approach to CBC collection would be appropriate.

Background:

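### Additional hemoglobins, signs of anemia and transfusion are recorded without times, so care that followed a routine POD1 CBC cannot be separated from care already prompted by clinical concern

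*Combined protocol and SAP*

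**What the plan says.** The Purpose of Study section sets the question: "To determine if checking a routine CBC results in clinically relevant changes to patient care". The end of the Background narrows the goal to showing that "routine collection of a CBC on POD1 in asymptomatic patients after vaginal hysterectomy with prolapse repair is unnecessary". It also describes the standing practice: patients stay overnight and "a CBC is collected the morning on POD1".

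The Data Collection section lists the variables that bear on this question:

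- The index test is "CBC collected the morning of POD1 – yes/no", together with the POD1 hemoglobin, the preoperative hemoglobin and the change between them.
- Further testing is "More than one postoperative hemoglobin obtained – yes/no".
- Signs of anemia are two yes/no items, one beginning "Patient with objective signs of anemia" and a parallel one for subjective signs.
- Downstream care is "Blood transfusion – yes/no" and "Delay in discharge due to CBC results – yes/no".

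No listed variable gives the time of a draw, the order of draws, the reason for an order, the value of any additional hemoglobin, the onset of signs, or the time of a transfusion. The section also refers to an attached data collection sheet, which is not among the documents.

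The Statistical Analysis section uses symptom status twice: to compare mean hemoglobin change between women with and without symptoms, and as the outcome of a logistic regression. It plans no tabulation of further tests, transfusion or delayed discharge by symptom status.

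**The concern.** If the routine draw were stopped, women who raise clinical concern would still be tested. What the study needs is therefore the added yield of the standing draw: care changes that followed it in women who had given no earlier reason for testing. Identifying those women requires the order of events, meaning whether concern, signs or another hemoglobin came before or after the POD1 result.

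The listed fields do not hold that order. The item on additional hemoglobins is the most exposed. The Background names more blood work as one of the things that can follow an abnormal result, so this item is a natural measure of what the CBC sets off. Yet it is positive both for a draw that came before the POD1 CBC and for one that the POD1 result prompted. Without a value for the additional draw, a stable recheck also cannot be told from a continuing fall.

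At stake is how the few women with further tests, transfusion or delayed discharge are classified. They decide whether the routine draw has any utility.

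**Working it through.** **Inputs.** The documents give an anticipated sample of about 800. It rests on case volume and on similar studies of 629 to 1105 patients, with no error rate, power or event rate. There is no formula to reproduce; 800 does lie within 629 to 1105. The documents give no expected number of transfusions, further tests or delayed discharges for this cohort, so the counts below are assumptions.

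**Step 1: histories that receive the same codes.** All four women below are hypothetical. Each has a POD1 CBC, more than one postoperative hemoglobin, and a transfusion.

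| Woman | What happened | POD1 CBC | More than one Hb | Signs | Transfusion |
|---|---|---|---|---|---|
| A | Signs on the evening of surgery, hemoglobin drawn then, standing morning CBC follows | yes | yes | yes | yes |
| B | No signs, low standing CBC, repeat drawn, signs charted only afterwards | yes | yes | yes | yes |
| C | Visible bleeding without a listed sign, early hemoglobin, standing morning CBC follows | yes | yes | no | yes |
| D | No signs at any time, low standing CBC, repeat drawn | yes | yes | no | yes |

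A and C would have been tested under a selective policy. B and D had no reason for testing before the standing draw. The fields pair A with B and C with D. Splitting on the signs items therefore puts B with the symptomatic women, which understates the yield of the routine draw, and C with the asymptomatic women, which overstates it. The POD1 value is recorded for all four but does not give the order of events.

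**Step 2: size if concern-driven care is counted.** Let E be the number of women with a care change and f the share in whom clinical concern came first. The apparent yield is E/800, and the yield that followed a routine draw is E(1 − f)/800. Exact (Clopper-Pearson) 95% intervals are in brackets.

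| E (assumed) | f = 0 (apparent yield) | f = 0.5 | f = 1 |
|---|---|---|---|
| 8 | 1.00% (0.43 to 1.96) | 0.50% (0.14 to 1.28) | 0% (0 to 0.46) |
| 24 | 3.00% (1.93 to 4.43) | 1.50% (0.78 to 2.61) | 0% (0 to 0.46) |
| 40 | 5.00% (3.60 to 6.75) | 2.50% (1.53 to 3.83) | 0% (0 to 0.46) |
| 80 | 10.00% (8.01 to 12.29) | 5.00% (3.60 to 6.75) | 0% (0 to 0.46) |

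The listed fields do not determine f, so they cannot say which column applies.

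**Step 3: size in the other direction.** Take E = 8 and suppose 4 women truly had no concern before the routine result: 4/800 = 0.50%. If 2 of those 4 had signs charted only afterwards, a tabulation restricted to women without signs shows 4 − 2 = 2, or 2/800 = 0.25%. If all 4 did, it shows 0. These splits are also assumed.

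**The case against.** Several points on the other side stand.

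- A reader might infer that the plan credits concern-driven care to routine testing. It does not. The Statistical Analysis section contains no count that attributes further tests, transfusion or delay to the CBC, and the item on additional hemoglobins does not claim that the POD1 result prompted them. The risk lies in how the data can later be read.
- Existing fields allow a partial split. Care changes can be tabulated in women without signs, and delay in discharge is already recorded as attributable to CBC results. But the signs are untimed, visible bleeding is not listed among them, and the delay item does not say whether the CBC was routine or prompted.
- The morning draw is standard practice, so most are probably routine. A woman with suspected bleeding would ordinarily have that draw too. Order reason alone is therefore a weak discriminator, and it may not be charted. Times and prior clinical status carry more information.
- Overstating the yield runs against the study's own hypothesis of minimal utility, so a low apparent yield would be reassuring. This holds for an unstratified count. It does not hold for a split on untimed signs, where women like B leave the asymptomatic group and the error favors the hypothesis.
- The illustrative counts are not evidence of how often this happens, and nothing in the documents says how often a hemoglobin is drawn before the POD1 CBC.
- The collection sheet is unseen. If it already records times and values, most of the point is settled.

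**Conclusion.** The point holds in a limited form. Among the listed variables, events before the POD1 CBC cannot be separated from events after it, so the added yield of the routine draw in asymptomatic women can be misstated in either direction. Its size cannot be fixed from the documents: for any apparent rate, the part that followed a routine draw lies between zero and the whole of it. With the assumed 8 events in 800, that is 0% to 1.0%.

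Two stronger readings are not supported. One is that the study will necessarily overstate the value of routine testing; no planned analysis makes that count, and the error can go the other way. The other is that the study cannot address its question at all; the POD1 value is kept, and the signs and delay fields give a partial answer.

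The conclusion assumes that the unseen collection sheet adds no times or values, and that at least some women with further tests or transfusion had clinical concern before the morning draw. It is a cheap improvement worth making before abstraction, and it is not a fatal defect.

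**What to change.** Confirm first what the attached collection sheet already contains. Then add to the abstraction:

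1. date, time and value of every postoperative hemoglobin to discharge, in place of the yes/no item on additional draws;
2. whether signs of anemia, or a documented concern about bleeding, came before the POD1 CBC;
3. the time of any transfusion;
4. the order reason for each hemoglobin, where it is charted.

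In the Statistical Analysis section, add a table of repeat hemoglobins drawn after the POD1 result (split into further fall and stable), transfusion and delayed discharge. Give it separately for women with no signs, concern or hemoglobin before the POD1 CBC and for all other women, with counts and exact confidence intervals.

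The cost is a few more fields from charts that are already being opened one by one, and a somewhat smaller group for the main utility table. Order reason may be missing for some women; dates, times and values alone would still resolve the sequence of hemoglobins.

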Surgeons commonly check a CBC on patients after major gynecologic surgery. This is done to evaluate for postoperative anemia and to provide surgeon reassurance prior to discharging a patient home. There are more than 200,000 inpatient operative procedures completed for pelvic organ prolapse annually in the United States.⁵ Studies quote rates from, 87-99.6% of patients having a CBC drawn on POD1 and up to 1/3 of these patients requiring some intervention based on these results.^{6,7,11} Further evaluations of abnormal lab results may be additional blood work or more invasive procedures such as imaging tests or reoperation.

In recent years, multiple studies have shown that routine preoperative lab testing is not ubiquitously indicated for women undergoing gynecologic and urologic surgery. Thirty day outcomes do not change regardless of lab collection prior to surgery.³ The American Society of Anesthesia recommends against routine preoperative lab testing in the absence of clinical indications.¹⁴ Even with these recommendations, up to 40% of women receive un-indicated preoperative lab testing prior to urologic procedures.¹³ Similar to lab testing in the preoperative period, despite the high rate surgeons ordering postoperative labs, the clinical utility of a POD1 CBC has been called into question.

Throughout the gynecology literature, studies have identified multiple risk factors for a larger drop in hemoglobin on POD1 including hysterectomy at the time of pelvic surgery, midurethral sling placement at the time of prolapse repair, lower BMI, and the amount of IVF received in the OR.^{2,11} These findings were corroborated by additional studies, which also identified preoperative anemia, history of coagulopathy, and African American or Hispanic ethnicity as risk factors for postop blood transfusion.^{4,8,10,12} Although these patient and surgical characteristics have been identified as risk factors for postoperative anemia and transfusion, one study noted based on their data, that if they restricted CBC collection to patients with at 2 or more signs of anemia on POD1, 90% of their sample would not have required testing.⁷ Other studies have corroborated that almost all patients that ultimately require blood transfusion will show clinical signs of anemia.^{2,6,11}

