- There are no potential risks to the study population by any aspect of this study.

Statistical Analysis:

Demographic data will be described using frequency (percentage) for categorical variables and mean (standard deviation) or median (min, max) for continuous variables. The percentage of subjects with hemoglobin less than 10 g/dL at POD1 will be evaluated as well as the percentage of subjects with signs of anemia. Pearson product moment correlation coefficient will be employed to measure the association between postoperative hemoglobin level and perioperative variables such as age, BMI, blood loss, or length of surgery. The mean hemoglobin change from pre- to postoperative measurement in symptomatic subjects will be compared with that of asymptomatic subjects using Student's t-test. Multiple linear regression will be used to investigate risk factors impacting mean decrease in hemoglobin. On the other hand, multiple logistic regression will be used to investigate factors associated with the presence of signs of anemia.

Ethical Considerations:**Informed Consent:**

- Informed consent will not be required given the retrospective chart review design of this study.

Privacy Information:

- Extensive effort will be made to ensure and maintain participant confidentiality. All identifying information will be maintained in a secure area at all times. All communication between staff members regarding participant data will occur via the Subject ID number only. However, identifying information will be retained in the original/source documents.
- The Excel spreadsheet will be stored on a password protected, encrypted TriHealth computer for ten years following study closure, and then purged.

Cost/Budget:

- This study will incur no cost to the institution, the participants, or the investigators.

Estimated Period of Time to Complete Study	
When will study begin?	Winter 2019
Protocol Development Completed	2 weeks
Admin Review Time	2 weeks
IRB Approval	3 weeks
Data Collection	4 weeks
Data Analysis	2 weeks
Presentation Development (if applicable)	2 weeks
Manuscript Development (if applicable)	4 weeks
Journal Submission Process (if applicable)	4 weeks
Study Closure	2 weeks

When and how will results be disseminated?

- The results will be disseminated by way of an oral or poster presentation at a national meeting and with publication in a high-impact journal.

References:

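### Signs of anemia carry no timing relative to the POD1 CBC result, so signs first charted after a low result count towards symptomatic status

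*Combined protocol and SAP*

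**What the plan says.** The Data Collection section of the protocol lists two yes/no variables. One is "Patient with objective signs of anemia", defined by persistent pulse and blood-pressure changes. The other is "Patient with subjective signs of anemia", defined by a list of symptoms and appearances. Neither is placed in time relative to the CBC draw or its result. Other items in the same list are timed: the preoperative CBC has a 30-day window, the postoperative CBC is tied to POD1 morning, and readmissions and emergency visits have 30-day limits. The section opens with "Please see attached data collection sheet"; that sheet was not supplied.

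Statistical Analysis uses signs or symptom status three times. It reports the share with low hemoglobin "as well as the percentage of subjects with signs of anemia", compares hemoglobin change between symptomatic and asymptomatic subjects by t-test, and fits a logistic model for the presence of signs. It states no time window and does not define symptomatic. That the groups rest on the Data Collection signs is an inference, though no other listed variable could form them.

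The goal, at the end of Background, is to show that "routine collection of a CBC on POD1 in asymptomatic patients after vaginal hysterectomy with prolapse repair is unnecessary". The Hypothesis section adds that "a more selective approach to CBC collection would be appropriate".

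**The concern.** A selective testing policy needs a sign that is known without the CBC. The Background cites a rule of this kind: had the investigators of one study "restricted CBC collection to patients with at 2 or more signs of anemia on POD1, 90% of their sample would not have required testing". There the sign comes first and decides who is tested.

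In this cohort a POD1 CBC is standard practice and the data come from charts. A low result may lead staff to ask about dizziness or to note pallor. A woman with no sign until then would be entered as symptomatic, although she is one of the women in whom the routine test may have added information. She leaves the group that the goal concerns, and an untimed yes/no does not allow her to be identified afterwards.

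**Working it through.** **1. The plan's own figure.** The only relevant figure is the anticipated sample of about 800. It rests on case volume (800/5 = 160 a year) and lies within the cited range of 629 to 1105. No SD, effect size or power is given, so there is no planned t-test figure to reproduce, and nothing below changes the 800.

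**2. What follows without a model.** Let n_pre be the women with a sign charted before the result and n_post those whose first sign is charted after it. The untimed definition counts n_pre + n_post. The percentage with signs therefore exceeds the pre-result percentage by 100 × n_post/N, which is never negative, and the asymptomatic group is smaller by n_post. Some of the n_post signs will be genuine.

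**3. Illustration on assumed inputs.**
- N = 800 (Sample Size section).
- True pre-result signs p = 0.10. This is in line with the cited study, in which 90% would not have needed testing (100 − 90 = 10%), but that study followed a different operation and required two or more signs.
- Hemoglobin drop has SD 1 g/dL, with mean 2 in sign-free women and 2 + d in women with true signs (assumed).
- A share f = 5, 10 or 20% of sign-free women with a low result is relabelled (assumed; the documents give no rate).
- Low is taken as a drop >4, a drop >3, or the protocol's own marks: a drop ≥2, or Hb ≤10 (with preoperative Hb assumed to have mean 13 and SD 1, independent of the drop).

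Let q be the probability of a low result in sign-free women, e their mean drop given a low result, and r = (1 − p) × q × f.

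Change in the symptomatic-minus-asymptomatic difference = r × [(e − 2 − d)/(p + r) + (e − 2)/(1 − p − r)].

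Example (drop >3, f = 10%, d = 0): q = 0.1587 and e = 3.525, so r = 0.9 × 0.1587 × 0.10 = 0.01428. Women moved: 800 × 0.01428 = 11.4. Percentage with signs: 100 × (0.10 + 0.01428) = 11.4%. Change: 0.01428 × (1.525/0.11428 + 1.525/0.88572) = 0.215 g/dL.

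Each cell gives f = 5/10/20%; changes are in g/dL.

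| Low result | q | e | Women moved | % with signs | Change, d = 0 | Change, d = 1.0 | Change, d = 1.5 |
|---|---|---|---|---|---|---|---|
| Drop >4 | 0.0228 | 4.373 | 1/2/3 | 10.1/10.2/10.4 | 0.027/0.053/0.104 | 0.017/0.033/0.065 | 0.012/0.023/0.045 |
| Drop >3 | 0.1587 | 3.525 | 6/11/23 | 10.7/11.4/12.9 | 0.114/0.215/0.389 | 0.047/0.090/0.167 | 0.014/0.028/0.056 |
| Drop ≥2 | 0.500 | 2.798 | 18/36/72 | 12.3/14.5/19.0 | 0.167/0.290/0.467 | −0.017/−0.021/−0.007 | −0.109/−0.176/−0.244 |
| Hb ≤10 | 0.240 | 2.916 | 9/17/35 | 11.1/12.2/14.3 | 0.100/0.185/0.322 | 0.003/0.008/0.021 | −0.046/−0.081/−0.130 |

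The formula has two terms. Relabelling pulls the symptomatic mean towards e, and it always lowers the asymptomatic mean here because e > 2. The difference can therefore grow slightly even when relabelled women have smaller drops than truly symptomatic women. In the Hb ≤10 row at d = 1.0, e is 2.916 against 3.0, and the change is still positive.

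**4. Significance of the t-test.** In simulation of the same model, with low taken as a drop >2, >3 or >4, the test without relabelling rejects in about 99% of studies at d = 0.5 and 100% at d = 1.0 or 1.5. With relabelling it rejects in 99 to 100%. At d = 0.25 rejection rises from about 56% to between 64 and 100%.

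**The case against.** The strongest reply is that the mechanism is assumed. No passage says that charting responds to results, and the 5 to 20% rates have no source. The stay is overnight with the CBC on POD1 morning, so the inpatient time after the result may be short. A persistent pulse or blood-pressure change is less open to prompting than a reported symptom. The data collection sheet may already carry times. Statistical Analysis plans no outcome analysis within asymptomatic women, so among its outputs only the percentage with signs has a bias of known direction. The remedy also sorts by time of charting, not of occurrence, so a true early sign written up late is misplaced.

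All of this stands as a limit on weight. It does not supply a timing rule for the analysis, and the goal still concerns women who are asymptomatic without the result.

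Three stronger readings are tempting and are not supported:
- A reader might infer that the t-test will reject far more often than its nominal 5% when there is no true difference. That requires signs to be unrelated to hemoglobin drop. The Background points the other way, since it cites studies in which nearly all transfused patients showed signs.
- A reader might infer that the symptomatic-asymptomatic difference will be exaggerated. The table shows that it can also be nearly unchanged or reduced.
- A reader might infer that timing was never collected. Without the sheet, this cannot be said.

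**Conclusion.** The point holds as a gap in the stated definition. The protocol text gives no timing for signs of anemia, and the analysis text gives no rule, while three planned analyses depend on them. The one-way consequences (a higher percentage with signs and a smaller asymptomatic group) follow from counting alone. Their size depends on how often charting is prompted by the result, which the documents do not show. In the illustration the percentage with signs goes from 10% to 10.1–12.9% if only drops above 3 or 4 g/dL prompt charting, and up to 19.0% if drops of 2 g/dL or more do.

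The effect on the hemoglobin-change difference is of unknown size and direction, and the test's significance would hardly change if the true difference is about 0.5 g/dL or more. The logistic outcome is exposed to the same relabelling; its effect is not sized here. This is a cheap improvement that should be made, not a defect that invalidates the study. Confidence is medium, because the sheet is unseen and the link between symptomatic status and the listed signs is inferred.

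**What to change.** For each woman with a sign, record whether the first qualifying sign was charted before or after release of the POD1 CBC result, using times on the attached sheet if it has them. Release is the cut point because charting can respond to the result only once it is known.

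State in Statistical Analysis that symptomatic means a qualifying objective or subjective sign charted after surgery and before the result. Report signs first charted after the result, or in an order that cannot be determined, as a separate category, and say how that category enters the two-group test. A woman whose first sign is known to follow the result was sign-free when it arrived, and omitting her would still remove her from the group the goal concerns. Show the percentage with signs, the t-test and the logistic model under the any-time definition as a sensitivity analysis.

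The cost is one field. At an assumed 1 to 3 minutes a chart, applying it to all 800 charts takes 800/60 = 13 to 2400/60 = 40 hours within the planned four weeks of data collection. If it is needed only where a sign is present (80 charts at 10%), it takes 80/60 = 1.3 to 240/60 = 4 hours. The downside is that genuine signs charted late fall into the separate category, which is why both definitions are shown.
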